#### 7.2.1 Physical Examination

Physical examinations will include assessments of the head and neck, heart, lungs, abdomen, extremities, neurological and skin.

### 7.2.2 Vital Signs, Weight and Height

Vital signs will include heart rate, respirations, blood pressure, temperature, and weight. All vital signs should be measured after the subject has been sitting/resting for at least 5 minutes. For adult subjects (>18 years), measurements of height obtained within the prior 6 months may be utilized. In the event of an infusion reaction or hypersensitivity reaction, vital signs should be monitored more frequently than originally scheduled and as clinically indicated.

Weight will be measured at the times indicated, preferably without outer garments such as hats, coats or shoes. Measurements while in light indoor clothing only, or undergarments only, are acceptable; but every effort should be made to measure subjects in the same or similar clothing, including any accessories or jewelry, at each assessment.

### 7.2.3 Clinical Laboratory Tests

Laboratory assessments will be performed to evaluate safety at scheduled time points (refer to [Appendix 13.1](#)) during the course of the study. The following assessments will be performed at the local laboratory:

- CBC, including white blood cell (WBC) count with five-part differential (neutrophils, lymphocytes, monocytes, eosinophils, and basophils), red blood cell (RBC) **count**, platelet count, hemoglobin, and hematocrit.
- Chemistry panel, including electrolytes (sodium, potassium, chloride, and carbon dioxide), creatinine, blood urea nitrogen (BUN), calcium, phosphorus, magnesium, estimated glomerular filtration rate, glucose, albumin, total protein, amylase, lipase, and liver function tests (total and direct bilirubin, ALT, AST, alkaline phosphatase, lactate dehydrogenase [LDH]).
- Coagulation tests, including prothrombin time (PT), activated partial thromboplastin time (aPTT)/partial thromboplastin time (PTT), and INR.
- Urinalysis, including dipstick results for color, appearance, specific gravity, pH, glucose, bilirubin, ketones, occult blood, and protein; as well as untimed (spot) analysis of protein and creatinine for ratio.
- Hepatitis B and C tests include Hep B surface antigen (HBsAg), Hep B surface antibody (HBsAb), Hep B core antibody (HBcAb) and hepatitis C virus (HCV) antibody. Results that may be consistent with chronic or active infection, and/or subjects with known prior active hepatitis B or C infection, should undergo polymerase chain reaction (PCR) tests for Hep B and/or C, respectively.
- Pregnancy test, consisting of blood or urine testing for beta-human chorionic gonadotropin ( $\beta$ -hCG). Repeat testing may be performed as requested by the Investigator.

#### **7.2.4 Electrocardiograms**

Throughout the study, subjects will be monitored for changes in cardiac conduction through ECGs. ECGs will be done in triplicate at the times indicated in [Appendices 13.1](#) and [13.2](#).

#### **7.2.5 Echocardiogram**

ECHOs will be performed at the indicated times ([Appendix 13.1](#)) to assess any pericardial effusions, if present, as well as cardiac function (left ventricular ejection fraction, LVEF).

#### **7.2.6 ECOG Performance Status**

ECOG performance Status ([Appendix 13.3](#)) will be evaluated at protocol-specific time points ([Appendix 13.1](#)).

#### **7.2.7 Fluid Retention Questionnaire**

Throughout the treatment period, subjects will be asked about the development of any new or worsening peripheral edema or dyspnea ([Appendix 13.9](#)). This assessment may take place virtually (e.g., by phone).

#### **7.2.8 Daily Weight Diary**

Throughout the treatment period, subjects will maintain a diary of daily weights.

#### **7.2.9 Pregnancy Testing**

In WOCBP, pregnancy testing will be conducted at scheduled time points during screening and the course of the study (refer to [Appendix 13.1](#)). Contraception recommendations are outlined in [Section 4.3](#).

### **7.3 Radiographic Response/Efficacy Assessments**

Radiographic evaluations at protocol-specified time points include:

- CT scans of the chest, abdomen and pelvis (scans of the neck must also be obtained for MTC and/or if there is documented or suspected involvement in this region)
- MRI of the brain, if indicated. CT of the brain with intravenous contrast may be substituted at the discretion of the Investigator.
- Whole-body technetium-99m (99mTc) bone scintigraphy (prostate cancer subjects only)

Diagnostic quality, spiral CT scans are recommended; other methods may be used if performed consistently throughout the study for each individual subject. Positron emission tomography (PET) and/or octreotide/somatostatin scans may be used in an ancillary manner; however, no decisions relating to PD may be made based on PET or octreotide/somatostatin scans alone. Clinical response will be determined by the Investigator at each assessment according to RECIST v1.1 ([Appendix 13.6](#); [Eisenhauer 2009](#)), and/or for prostate cancer subjects, PCWG3 criteria ([Appendix 13.7](#)).

For tumors to be assigned a status of responder (PR or CR), changes in tumor measurements must be confirmed by repeat assessments performed no less than 4 weeks, but preferably not more than 6 weeks, after the criteria for response are first met; i.e., two consecutive assessments of PR or CR are required. In instances where a follow-up visit is not otherwise scheduled to occur for more than 6 weeks, repeat radiographic disease assessments should be conducted at least 4 but not more than 6 weeks after the criteria for response are first met, in order to confirm response, whether or not a formal follow-up visit is conducted at the same time.

### 7.3.1 Radiographic Disease Progression

Radiographic PD will be defined as either of the following:

- PD by RECIST v1.1 (refer to [Appendix 13.6](#))
- Confirmed PD by Bone Scan (for prostate cancer subjects using PCWG3 criteria; [Appendix 13.7](#))

Treatment beyond what would be considered PD using RECIST v1.1 or PCWG3 is permitted if the following criteria, as assessed by the Investigator, are met:

- Ongoing clinical benefit, without rapid PD
- Subject continues to meet all other study protocol eligibility criteria
- Tolerance of study drug
- Stable ECOG performance status

Treatment beyond progression must not delay an imminent intervention to prevent serious complications of PD (e.g., CNS metastases).

Subjects' clinical data must be available for CRF source verification. Copies of tumor images must be made available for review by the Sponsor or its designee upon request.

### 7.3.2 Patient Reported Outcomes

PROs will be evaluated for subjects in Part B of the study (only) by assessment of health-related quality of life and symptoms using the EORTC QLQ-C30 and EQ-5D-5L questionnaires. The questionnaires will be completed during screening, Cycle 2 (Days 1 and 29), and EOT (as outlined in the Schedule of Assessments [Appendix 13.1](#)). Additional details regarding the questionnaires are provided in [Section 10.3.9](#).

## 7.4 Pharmacokinetic Assessments

Blood samples for PK and ATA testing will be collected throughout the study as indicated in [Appendices 13.1](#) and [13.2](#).

Sensitive, qualified assays will be used to measure plasma concentrations of rovalpituzumab tesirine ADC (SC16LD6.5). Plasma concentrations of rovalpituzumab total antibody and blood concentrations of SC-DR002, the small molecule component of rovalpituzumab tesirine, may

also be measured if deemed necessary and appropriate. A qualified immunoassay will be used to assess ATA against rovalpituzumab tesirine.

## **7.5 Pharmacodynamic and Biomarker Assessments**

Blood and/or tissue samples for pharmacodynamics and biomarker testing will be collected at the time points throughout the study as indicated in [Appendices 13.1](#) and [13.2](#). Refer to the laboratory manual for additional details.

AbbVie (or people or companies working with AbbVie) will store the samples in a secure storage space with adequate measures to protect confidentiality. The samples may be retained while research on rovalpituzumab tesirine (or drugs of this class) or this disease and related conditions continues, but for no longer than 20 years after study completion, or per local requirement.

### **7.5.1 Tumor Tissue**

Tumor tissue, consisting of a representative archived specimen, or a fresh tumor biopsy, will be assessed at baseline for expression of DLL3 by methods such as but not necessarily limited to immunohistochemistry ([Section 7.1.1](#)). Additional studies, such as routine hematoxylin and eosin for morphology and histological classification, IHC for confirmation of diagnosis (e.g., for synaptophysin, chromogranin-A, or CD56 for neuroendocrine tumors, or HMB45, S100, or MART-1 for melanoma), or scoring of immune infiltrates (e.g., IHC for CD3+, CD4+, CD8+, and Foxp3+ cells) may be performed. Tumor material may also be utilized for exploratory research that includes assessments of nucleic acid or protein based biomarkers of drug sensitivity, resistance, or disease biology and development of a companion diagnostic assay.

At PD, an optional tumor biopsy may be performed for the assessment of expression of DLL3 and/or execution of additional studies, such as but not necessarily limited to scoring of immune infiltrates or assessment of molecular pathways related to the response to rovalpituzumab tesirine. Tumor material may also be utilized for exploratory research that includes assessments of nucleic acid or protein based biomarkers of drug sensitivity, resistance, or disease biology and development of a companion diagnostic assay. Additional instructions will be provided in the laboratory manual.

### **7.5.2 Inflammatory Markers**

At the indicated times, blood will be collected for local testing of inflammatory markers, including erythrocyte sedimentation rate (ESR), C-reactive protein (CRP), antinuclear antibodies (ANA), and rheumatoid factor (RF).

### **7.5.3 Blood Tumor Markers**

At the indicated times, blood will be collected for testing of tumor-specific biomarkers, including but not necessarily limited to, the disease-specific biomarkers in [Table 7-1](#).

**Table 7-1 Disease-Specific Blood Tumor Markers**

*Note: Blood tumor markers are NOT collected for Cohort 8, Other Solid Tumors.*

Tumor	Calcitonin	CEA	CgA	LDH	NSE	PSA	S100B
Melanoma				X			X
MTC	X	X					
All NECs (Cohorts 4, 5, 6, and 7)		X	X		X	X a	

Abbreviations: CEA = carcinoembryonic antigen; CgA = chromogranin A; LDH = lactate dehydrogenase; MTC = medullary thyroid carcinoma; NEC = neuroendocrine carcinoma; NSE = neuron-specific enolase; PSA = prostate-specific antigen; S100B = S-100 calcium-binding protein B.

a Required for prostate cancer subjects only.

#### 7.5.4 Soluble Biomarkers

At the indicated times, blood samples will be collected for possible testing of biomarkers that may be related to the pharmacodynamics effects of rovalpituzumab tesirine, such as but not necessarily limited to, soluble DLL3, or circulating chemokines or cytokines such as vascular endothelial growth factor (VEGF), epidermal growth factor (EGF), interleukin (IL)-6 or IL-8.

#### 7.5.5 Circulating Tumor Cells

At the indicated times, blood samples from subjects with neuroendocrine prostate cancer will be collected for assessment and characterization of CTC as a possible reflection of disease burden for central processing at all sites. A sample for exploratory analyses of CTC-associated biomarkers, such as DLL3, will be collected from subjects with large cell neuroendocrine carcinoma (cohort 4), neuroendocrine prostate cancer (cohort 5), and high-grade gastroenteropancreatic neuroendocrine carcinoma (cohort 6).

#### 7.5.6 Serosal Fluid

Any pericardial, pleural and/or ascitic fluid collected as part of routine care (e.g., as part of a therapeutic thoracentesis, pericardiocentesis, or paracentesis) will be procured, where feasible, for possible PK, pharmacodynamic and/or biomarker testing. Refer to the laboratory manual for additional details. For clinical serosal effusions, refer to [Section 7.2.3](#).

#### 7.5.7 Biospecimen Repository

For subjects who provide additional written consent, remaining de-identified unused clinical samples (blood and/or tissue) will be retained by the Sponsor and used for the Sponsor’s future research, including, but not limited to, the evaluation of DLL3 and of additional targets for novel therapeutic agents, the biology of DLL3, and to identify biomarkers. Blood and tissue samples donated for future research may be retained by the Sponsor or its designee indefinitely or as permitted by the applicable laws and regulations in the relevant country in which the study is conducted. If additional written consent is not provided, any remaining biological samples will be destroyed by Sponsor or its designee following study completion.

## 8. Complaints

A complaint is any written, electronic, or oral communication that alleges deficiencies related to the physical characteristics, identity, quality, purity, potency, durability, reliability, safety, effectiveness, or performance of a product/device after it is released for distribution.

The investigational product in this study is defined as rovalpituzumab tesirine. Complaints associated with any component of this investigational regimen must be reported to the Sponsor (Section 8). For AEs, please refer to Section 8.1. For product complaints, please refer to Section 8.2.

### 8.1 Medical Complaints

The Investigator will monitor each subject for clinical and laboratory evidence of AEs on a routine basis throughout the study. The Investigator will assess and record any AE in detail, including the date of onset, event diagnosis (if known) or sign/symptom, severity, time course (end date, ongoing, intermittent), relationship of the AE to study drugs, and any action(s) taken. For SAEs considered as having "no reasonable possibility" of being associated with study drugs, the Investigator will provide another cause of the event. For AEs to be considered intermittent, the events must be of similar nature and severity. AEs, whether in response to a query, observed by site personnel, or reported spontaneously by the subject will be recorded.

All AEs will be followed to a satisfactory conclusion.

#### 8.1.1 Definitions

##### 8.1.1.1 Adverse Events

An AE is defined as any untoward medical occurrence in a patient or clinical investigation subject administered a pharmaceutical product and which does not necessarily have a causal relationship with this treatment. An AE can therefore be any unfavorable and unintended sign (including an abnormal laboratory finding), symptom, or disease temporally associated with the use of a medicinal (investigational) product, whether or not the event is considered causally related to the use of the product.

Such an event can result from use of the drug as stipulated in the protocol or labeling, as well as from accidental or intentional overdose, drug abuse, or drug withdrawal. Any worsening of a pre-existing condition or illness is considered an AE.

Worsening in severity of a reported AE should be reported as a new AE. Laboratory abnormalities and changes in vital signs are considered to be AEs only if they result in discontinuation from the study, necessitate therapeutic medical intervention (including interruption/dose reduction of study drug, starting or discontinuing medication, etc.), meets protocol specific criteria (refer to Sections 5.5 and 8.1 regarding toxicity management) and/or if the Investigator considers them to be AEs.

An elective surgery/procedure scheduled to occur during a study will not be considered an AE if the surgery/procedure is being performed for a pre-existing condition and the surgery/procedure has been pre-planned prior to study entry. However, if the pre-existing condition deteriorates unexpectedly during the study (e.g., surgery performed earlier than planned), then the deterioration of the condition for which the elective surgery/procedure is being done will be considered an AE.

All protocol-related AEs must be collected from the signing of the study specific informed consent until study drug administration.

In addition, AEs with onset or worsening reported by a subject from the time that the first dose of study drug is administered until 70 days have elapsed following discontinuation of study drug administration will be considered as TEAEs.

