#### **4.4.2 Subject Discontinuation from Study**

Any subject may be discontinued from the study for any of the following reasons:

- Withdrawal by subject
- Death
- Physician decision
- Lost to follow-up
- Study terminated by Sponsor
- Other

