#### **5.2.4.2 Clinical Monitoring of Grade 3 or Grade 4 Adverse Events**

Subjects who experience Grade 3 or 4 non-laboratory AEs will require weekly or more frequent clinical assessments, as appropriate. The assessments should include review of AEs, concomitant medications, vital signs, weight, physical examination, ECOG performance status, laboratory and other testing, as clinically appropriate.

Subjects who experience Grade 3 or 4 hematologic AEs should have repeat complete blood count (CBC) assessment at least every 3 days or more frequently, as clinically appropriate, until resolution of hematologic toxicity to Grade 2 or lower.

Subjects who experience Grade 3 or 4 non-hematologic laboratory AEs will require more frequent laboratory assessments, as clinically appropriate, until resolution of the AEs.

Subjects who experience Grade 3 or 4 laboratory abnormalities may require more frequent laboratory assessments, as clinically appropriate.

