**Table 5-1 Toxicities Requiring Dose Reduction**

Toxicities Requiring 1 Dose Level Reduction at First Occurrence	

 
– 2nd occurrence = 2nd dose level reduction
 
– Discontinue after 2 dose level reductions
 
	
Serosal Effusions and Edema	
 
• Grade 2 or higher pericardial effusion
 
• Grade 2 or higher pleural effusion
 
• Grade 2 or higher ascites
 
• Grade 2 or higher peripheral edema
 

Hematology	
 
• Grade 3 thrombocytopenia (platelets <math><50.0\text{--}25.0 \times 10^9/\text{L}</math>)
 
• Grade 4 neutropenia (ANC <math><0.5 \times 10^9/\text{L}</math>) lasting more than 7 days
 
• Grade 3 or higher febrile neutropenia (with ANC <math><1.0 \times 10^9/\text{L}</math>) (concurrent fever <math>\geq 38.3^\circ\text{C}</math>)
 

Laboratory Abnormalities	
 
• Clinically significant Grade 3 or higher non-hematologic laboratory abnormality that does not resolve to Grade 0/1 or baseline within 7 days
 
• Any other Grade 3 or 4 laboratory abnormality considered clinically significant and treatment-related; adjustments to these guidelines may occur based on the clinical judgment of the Investigator and with approval of the Medical Monitor and Sponsor
 
• Grade 2 hypoalbuminemia
 

Other Adverse Events	
 
• Grade 3 photosensitivity reaction (Section 5.5.2)
 
• Grade 3 or Grade 4 nonlaboratory treatment-related toxicity, with the exception of fatigue, asthenia, nausea, or other manageable constitutional symptom
 

Toxicities Requiring 2 Dose Level Reductions at First Occurrence	

 
– Discontinue at second occurrence
 
	

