### **10.3.7.1 Treatment Emergent Adverse Events**

TEAEs reported during the study will be coded using a Medical Dictionary for Regulatory Activities (MedDRA) dictionary. Incidence of TEAEs will be summarized by disease and cohort and the following:

- System organ class and preferred term
- System organ class, preferred term and severity

These summaries will be presented for the following subsets:

- Serious adverse events
- All adverse events
- Drug-related adverse events
- Adverse events leading to treatment discontinuation

For tables reporting AEs by severity, if a subject has multiple occurrences of an AE with the same organ class and preferred term, the most severe event will be presented.

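### An untreated Grade 3/4 cytopenia that changes no dosing is an AE only at the Investigator's discretion, because the AE rule for laboratory values reaches no hematologic threshold

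*Combined protocol and SAP*

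**What the plan says.** Section 8.1.1.1 first gives a general AE definition that can include an abnormal laboratory finding. It then narrows this for laboratory values and vital signs, with four alternative routes:

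1. "Laboratory abnormalities and changes in vital signs are considered to be AEs only if they result in discontinuation from the study";
2. they "necessitate therapeutic medical intervention (including interruption/dose reduction of study drug, starting or discontinuing medication, etc";
3. and 4. the abnormality "meets protocol specific criteria (refer to Sections 5.5 and 8.1 regarding toxicity management) and/or if the Investigator considers them to be AEs".

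Two other parts of the protocol bear on the first route. Section 4.4.1 lists an adverse event among the reasons for stopping study drug. Section 4.4.2, which opens "Any subject may be discontinued from the study for any of the following reasons", does not list it; the nearest entries are physician decision and other. The analysis in Section 10.3.7.1 is also framed in terms of treatment: one of its TEAE subsets is "Adverse events leading to treatment discontinuation".

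On monitoring, Section 5.2.4.2 states "Subjects who experience Grade 3 or 4 hematologic AEs should have repeat complete blood count (CBC) assessment at least every 3 days" or more often, until the toxicity is Grade 2 or lower. The last sentence of the same section says only that Grade 3 or 4 laboratory abnormalities may need more frequent tests.

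**The concern.** Safety and tolerability is the primary objective (Section 2.1), and TEAE incidence by disease and cohort is its main summary (Section 10.3.7.1). Whether a low count becomes a TEAE should depend on the count. Under Section 8.1.1.1 it depends partly on what happens next. If the subject is dosed again and the count delays or reduces that dose, the event qualifies by rule. If the subject has had the last dose and nothing is done about the count, it qualifies only by judgement.

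Whether another dose is given depends largely on disease control, which may differ between tumor types and dose levels. Recording could then differ between groups for reasons unrelated to the drug's toxicity. Blood counts are not a side issue here: Section 1.2 names thrombocytopenia as the most frequent drug-related event of Grade 3 or worse in both earlier SCLC studies, at 11% in each.

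**Working it through.** The plan states no figure on this point, so the check sets the passages side by side.

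**Where the hematologic thresholds are.** Section 3.1.3 defines DLTs by grade, duration or rescue for platelets and neutrophils, and by grade for anemia. Table 5-1, in Section 5.2.4.3, has a hematology row that opens "Grade 3 thrombocytopenia (platelets" and gives a range of below 50.0 to 25.0 × 10⁹/L. It also lists Grade 4 neutropenia beyond 7 days, febrile neutropenia and, under the two-level reductions, Grade 4 thrombocytopenia.

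**What the cross-reference reaches.** Section 5.5 covers effusions, skin reactions, liver injury, edema and pneumonitis. Its numerical laboratory limits are hepatic (Section 5.5.3). It points on to Section 5.2.4 or Table 5-1 for effusions, skin reactions and pneumonitis, but not for cytopenias. Section 8.1 is the section in which the sentence itself stands; its parts on definitions, severity, causality, deaths and collection period set no count threshold. I have not seen the text of Section 8.1.6 (Adverse Event Reporting) and assume that it adds none.

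**A Grade 3/4 cytopenia taken through the four routes.**

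| Situation | Status under Section 8.1.1.1 |
|---|---|
| A later dose is delayed or reduced because of the count | AE by rule (route 2) |
| No later dose, but a transfusion, growth factor or other medication is given (allowed by Section 5.4.2) | AE by rule (route 2) |
| Study drug is stopped because of the count | Reasonably an AE under route 2, though permanent stopping of study drug is not named; route 1 applies only if the subject also leaves the study |
| Study drug is stopped for another reason such as progression; count untreated, no medication changed | AE only if the Investigator considers it one (route 4) |

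The first and last rows can describe the same platelet count. They differ because the reduction in Section 5.2.4.3 takes effect in later cycles, so it cannot occur after a last dose.

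**Whether the laboratory tables close the gap.** Section 10.3.7.2 summarizes values and changes at each visit, with shift tables for chemistry and hematology and a listing of out-of-range and clinically significant values, whether or not they are AEs. The classification is by laboratory normal range. A platelet count just below the lower limit and one below 25 × 10⁹/L (Grade 4 in Appendix 13.8) both fall in the low category. Section 8.3 grades laboratory data by CTCAE when applicable, but Section 10.3.7.2 plans no table by grade.

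**The case against.** The strongest reply is that four routes joined by and/or catch nearly everything that matters. Treatment of any kind qualifies, stopping study drug for toxicity fits the open-ended wording of route 2, and an Investigator will rarely ignore a Grade 4 count. The TEAE window runs to 70 days after study drug ends and requires no later dose. Laboratory values are summarized and listed in any case. Table 5-1 does not abolish judgement either, since several of its laboratory entries turn on clinical significance or relation to treatment.

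Much of this stands, and it rules out three stronger readings that a reader might infer:

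- **That a cytopenia is a TEAE only if another dose follows.** Transfusion, growth factor, a change of medication or Investigator judgement each suffices without a further dose.
- **That DLT counting is affected.** Section 3.1.3 defines laboratory DLTs directly, without passing through Section 8.1.1.1, and they are summarized on their own DLT-Evaluable Set. Blood counts are also scheduled on Days 8, 15 and 29 regardless of AE status (Section 6.3.5; the Day 8 visit may become virtual from Cycle 5).
- **That the loss can be sized by discounting the 11% in Section 1.2.** Those are AE rates already recorded in other studies, under capture rules that the documents do not show. No mean number of doses is given for this study.

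The reply does not remove the last row of the table. Judgement is a weaker and less uniform route than a rule, and the normal-range tables do not recover the grade.

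**Conclusion.** The concern holds in a limited form. A Grade 3/4 cytopenia that is untreated and changes no dosing is recorded as an AE only at the Investigator's discretion, while the same value is an AE by rule when it delays or reduces a later dose. The causes are a first route that names leaving the study rather than stopping study drug, and a cross-reference without a hematologic threshold. Capture of laboratory toxicity as TEAEs may therefore be uneven across cohorts and dose levels.

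The size cannot be estimated from the documents. It depends on how often such counts occur after a last dose, how many are treated, and how often Investigators record the rest. That faster-progressing cohorts are affected most is plausible but not shown. The finding assumes that Section 8.1.6 adds no hematologic criterion. It is worth correcting because it concerns the primary objective and costs little.

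**What to change.** - **Section 8.1.1.1, first route:** name discontinuation of study drug, in line with Sections 4.4.1 and 10.3.7.1.
- **Section 8.1.1.1, cross-reference:** add Section 3.1.3 and Section 5.2.4 with Table 5-1, and state that a laboratory value meeting one of those thresholds is recorded as an AE whether or not another dose is given. Because Section 3.1.3 is confined to the first 3 weeks of Cycle 1 in Part A, say whether its thresholds serve for AE recording in later cycles and in Part B; Table 5-1 already applies to both parts.
- **Section 10.3.7.2:** add a summary of laboratory data by worst post-baseline CTCAE grade. This is needed even with the new cross-reference, because some values, such as Grade 3 neutropenia without fever, have no threshold of their own in either place.
- **Section 5.2.4.2:** reconcile the sentence on hematologic AEs, which says repeat counts should be done, with the sentence on laboratory abnormalities, which says more frequent tests may be required. Which monitoring rule applies is for the sponsor to settle.

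The cost is wording in two sections, a few more AE entries and one more table.
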